2.2. Pooling Algorithm

No pooling by country will be done for by-country analysis.

2.3. Analysis set and Analysis Phase

Each analysis involves the following 2 aspects: 1) analysis set, specifying the subjects to be included; and 2) analysis phase, specifying the time window within which data will be included.

Key analysis sets and analysis phases are defined below.

Analysis sets

- Intention-to-Treat (ITT) (as termed Full Analysis Set in the International Conference on Harmonisation [ICH] E9 guideline): This analysis set consists of all randomized subjects who have a signed valid informed consent.
- Per-Protocol (PP): This analysis set is a subset of the ITT analysis set.

Subjects with the key protocol deviations will be excluded from the PP analysis set. The categories and terms of the key protocol deviations will include the following:

- Did not meet the following inclusion or met the following exclusion criteria;
 - INT-2, INT-3, INT-4: subject with index hospitalization > 14 days, inclusion criteria 1, 2, 4, 6, exclusion criteria 10, 11, 14, 22, 24, 27
 - INT-6, INT-7: inclusion criteria 1.2, 2.2, 4.3, 6.1, exclusion criteria 10.2, 11.1, 14.1, 22.2, 24.2 without c
- Did not take any assigned study drug or took wrong study drug
- Did not discontinue study drug permanently according to the protocol (The subject becomes pregnant, develops any condition which requires permanent anticoagulation, has a fall in CrCl to below 20 mL/min during the study, or has a hemorrhagic stroke or intracranial bleeding)
- Had been taking prohibited concomitant therapies as specified in the protocol
 - INT-2: 2, 3,
 - INT-3, INT-4: 2, 3, 4, 6, 7, 8
 - INT-6, INT-7: 2.2, 3.2, 4.1, 7.1 without c and i

- Safety: This analysis set is a subset of the ITT analysis set, consisting of subjects who receive at least one dose of study drug.

Analysis phases

- Up-to-Day-45: This analysis phase includes all data from randomization to Day 45 (inclusive).

For time to event analyses, subjects who do not have events to be analyzed on or before Day 45 will be censored on Day 45 or the last outcome-evaluation date whichever occurs first.

- On-Treatment: This analysis phase includes all data from randomization to 2 days after the last dose of the study drug (inclusive).

For time to event analyses, subjects who do not have events to be analyzed during this phase will be censored on the last dose + 2 or the last outcome-evaluation date whichever occurs first.

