11.1.1. Analysis Sets

- Intention-to-Treat (ITT) (as in the International Conference on Harmonisation [ICH] E9 guideline): This analysis set consists of all randomized subjects who have a signed valid informed consent.
- Per-Protocol (PP): This analysis set is a subset of the ITT analysis set. Subjects with key protocol deviations will be excluded from the PP analysis set. Key protocol deviations will be defined in the SAP.
- Safety: This analysis set is a subset of the ITT analysis set, consisting of subjects who receive at least 1 dose of study drug.

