2.1. Definition of Trial Dates

Trial reference start date: the date of randomization of the subject.

Trial reference end date: the date of the last trial-related procedure for the subject and is defined as the maximum of the following dates:

- Dates of all study-related visits (including scheduled or unscheduled visits)
- Dates of all study-related procedures, findings and events, including, but not limited to, adverse events, concomitant medications, disposition, clinical laboratories, vital signs, death

First dose date: the date on which the first dose of study drug is taken by the subject. If missing or incomplete for a subject who takes study drug, the first dose date is set to the earliest logically possible date on or after randomization. More specifically, the first dose date is defined as the maximum of the randomization date and the first day of the month if only day is missing, and is defined as the randomization date if day and month are missing.

Last dose date: the date on which the last dose of study drug is taken by the subject. If missing or incomplete for a subject who takes study drug, the last dose date is in general set to the latest logically possible date on or after the first dose date.

To ensure consistency with other data of the trial, more specifically, the above date will be further

- capped by (that is, taking the minimum with) Day 45 date, death date, trial reference end date, and the upper bound of the logically possible range if partial date is available, and
- further bounded below by (that is, taking the maximum with) the (imputed) first dose date, any complete temporary drug stop and re-start date, or the lower bound of the logically possible range.

Upper bound of the logically possible range is defined as the last day of the month if only day is missing and is defined as the last day of the following month after randomization if day and month are missing. Lower bound of the logically possible range is defined the maximum of the randomization date and the first day of the month if only day is missing and is defined as the randomization date if day and month are missing.

Last outcome-evaluation date: the date of last study visit (clinic/phone) while the subject is alive during which the outcome status is ascertained.

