4.6. Prior and Concomitant Medications

Medication will be coded using the Anatomical Therapeutic Chemical (ATC) dictionary. The prevalence of medication use by ATC term will be summarized by treatment group and by study phase (prior to the first dose of study drug, during the study drug therapy period, and after last dose of study drug [post-treatment]). A medication that starts prior to the first dose of study drug is considered as a prior medication. A medication with a use period overlapping with the period between the first and last dose of study drug is considered as a concomitant medication. A medication that starts after the day of the last dose of study drug is considered as a post-treatment medication. Note that a medication use can be categorized into multiple study phases if its use spans into more than one study phase. In such a case, the medication use will be included in more than one summary.

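### Does the per-protocol rule on prohibited anticoagulants drop VTE events because they were treated?

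*SAP*

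**What the plan says.** Protocol 11.1.1 leaves the PP exclusions to the SAP: "Key protocol deviations will be defined in the SAP". SAP 2.3 then lists the categories. One is "Had been taking prohibited concomitant therapies as specified in the protocol", followed by item numbers for each protocol version. For the current versions the list reads "INT-6, INT-7: 2.2, 3.2, 4.1, 7.1 without c and i". Item 4.1 in Protocol 4.3 is the anticoagulant prohibition. The bullet sets no date limit and does not mention interruptions.

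The bullet just before it is "Did not discontinue study drug permanently according to the protocol". Its examples include a subject who develops a condition needing permanent anticoagulation.

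The PP set is used in sensitivity analysis b of SAP 5.2.2, together with the on-treatment phase, which runs from randomization to two days after the last dose. The primary analysis uses the ITT set up to Day 45.

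Two other SAP passages bear on dates. SAP 4.6 sorts medications for summary tables: "A medication with a use period overlapping with the period between the first and last dose of study drug is considered as a concomitant medication", whereas "A medication that starts after the day of the last dose of study drug is considered as a post-treatment medication". SAP 2.1 deals with a missing or partial last-dose date: "the last dose date is in general set to the latest logically possible date on or after the first dose date". It caps that date at Day 45, death, the trial reference end date and the end of the known month, but not at a non-fatal outcome.

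**The concern.** Anticoagulation is the usual consequence of a diagnosed VTE. If receiving it removes the subject from the PP set, inclusion in analysis b depends on the outcome. Suppose a subject takes the day's tablet, is diagnosed and starts an anticoagulant that evening. Under the SAP 4.6 overlap definition the anticoagulant is concomitant and the subject is removed, although the event lies inside the on-treatment window. The same VTE treated from the next morning is post-treatment and stays in. VTE-related deaths without anticoagulation are never removed this way, so the mix of components could shift.

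Two further groups could be caught. One is subjects with an incomplete last-dose date, where imputation creates an apparent overlap. The other is subjects anticoagulated during an interruption that Protocol 10.2.1 calls for, who then resume study drug. At stake are the precision of the planned consistency check and possibly its point estimate. SAP 4.2 and 4.3 do use the primary event date in defining completers and compliance, so its absence here looks like an oversight.

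**Working it through.** **1. What counts as a deviation.** The SAP 2.3 list is a list of key protocol deviations, and the bullet refers back to the protocol for what is prohibited. Three places fix the meaning:

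- The opening of Protocol 4.3 says what happens when a subject needs a prohibited drug: study drug is interrupted or stopped.
- Item 4.1 bars anticoagulants as concomitant therapy. Its second sentence provides for study drug to be discontinued when a condition such as VTE needs longer anticoagulation.
- The neighbouring SAP 2.3 bullet removes subjects who failed to stop study drug when permanent anticoagulation was needed. If anticoagulation alone were the deviation, that example would be largely redundant.

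Together these mean that the deviation is taking the prohibited drug alongside study drug. Stopping study drug and treating a VTE is compliance, and so is interrupting study drug for anticoagulation during a re-hospitalization.

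**2. What the other reading needs.** It needs SAP 4.6 to govern SAP 2.3. SAP 4.6 sorts drugs into study phases for prevalence tables by ATC term, and SAP 2.3 does not refer to it. If it is imported anyway, the outcome-linked losses are starts on the last-dose day and false overlaps from imputed dates. An example of the second: randomization on 22 February 2017 (Day 1), true last dose 3 March (Day 10), day missing, anticoagulant from 4 March. The imputed last dose is 31 March (Day 38), a false overlap of 28 days (4 to 31 March). This can happen, but it needs both an incomplete date and anticoagulation in the gap.

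**3. The plan's own figure.** Inputs from SAP 1.4: hazard ratio 0.60, two-sided 0.05, power 90%, 1:1 allocation. Events = 4(1.960 + 1.282)² / (ln 0.60)² = 161.07, which agrees with the stated 161.

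**4. Loss of precision.** The documents do not give the share of events affected, so these are assumptions. Let s be the share of events that are non-fatal VTE and r the share of those removed. Events left are d = 161(1 − s·r), and the 95% CI is 0.60·exp(±1.96·2/√d). With s = 0.5:

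| r | d | 95% CI around 0.60 |
|---|---|---|
| 0 | 161 | 0.44–0.82 |
| 0.10 | 153 | 0.44–0.82 |
| 0.25 | 141 | 0.43–0.83 |
| 0.50 | 121 | 0.42–0.86 |
| 0.75 | 101 | 0.41–0.89 |

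Nothing in the documents supports the lower rows for a route made up of same-day starts and occasional imputed dates.

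**5. Shift in the estimate.** Take 50 non-fatal events and 50 deaths per 4,000 on placebo, multiply each component by its hazard ratio for rivaroxaban, and drop removed subjects from numerator and denominator. The table gives the ratio of the remaining proportions.

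| Assumed HR, non-fatal / death | r = 0.10 | 0.25 | 0.50 | 0.75 |
|---|---|---|---|---|
| 0.6 / 0.6 | 0.600 | 0.599 | 0.598 | 0.598 |
| 0.5 / 0.7 | 0.605 | 0.613 | 0.631 | 0.657 |
| 0.7 / 0.5 | 0.595 | 0.585 | 0.566 | 0.538 |

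The direction follows the assumption chosen. Unequal removal by arm would also move the estimate. At 161 events, 100.6 are expected on placebo and 60.4 on rivaroxaban. Losing 20% of placebo and 10% of rivaroxaban events gives 54.3/80.5 = 0.675; losing 10% and 20% gives 48.3/90.6 = 0.533. Treatment is double-blind, and whether an anticoagulant starts on the last-dose day or the next has no evident link to arm.

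**6. Would a date rule be cleaner?** Not clearly. Exempting anticoagulation during interruptions would keep, in an on-treatment comparison, placebo subjects who received an active anticoagulant. The failure-to-stop bullet has no event-date limit either, so a limit on the anticoagulant bullet alone would not remove all post-event exclusions. Protocol 8 asks for identity and dose of anticoagulants but only identity for prohibited drugs other than NSAIDs, so the start dates that the comparison needs may not all be held.

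**The case for a change.** The best case for a change is that the SAP authors edited this list closely, carving out 7.1 c and i, yet said nothing about treatment of the outcome. Two programmers could build different PP sets. If SAP 4.6 does not apply, concomitant has no definition for this purpose, and item 4.1 taken literally reaches any anticoagulant used during the study, which would remove nearly every treated VTE. Events are scarcer than planned (Amendment INT-7), and a sentence before unblinding costs little.

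Part of this stands: SAP 2.3 does not state the rule, and a same-day start is ambiguous on its face. The literal reading does not stand, because item 4.1 names VTE and says what then happens to study drug; an analyst could not call that course a deviation. The argument about two programmers is weak for the same reason. Subjects anticoagulated during an interruption are a matter of choice, since a PP set may reasonably keep them or leave them out, and most have no VTE.

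**Conclusion.** No change follows. SAP 2.3 leaves a small gap, and the protocol text it points to fills it: anticoagulation given with study drug stopped or interrupted, as the protocol provides, is not a key deviation. What remains is a handful of possible same-day starts and imputed dates in one sensitivity analysis that has no power target. With 10% of non-fatal VTE removed, the interval is unchanged to two decimals. With a common effect and equal removal in both arms, the hazard ratio stays near 0.60. Larger effects need removal shares, component effects or differences between arms that the documents do not support. Every primary event up to Day 45 still counts in the ITT analysis that decides the trial.

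This rests on the INT-6 and INT-7 item wording; the older item texts cited for INT-2 to INT-4 are not in the documents. It also rests on analysts reading the bullet as a list of deviations, which is what SAP 2.3 calls it.

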10.2.3. Permanent Discontinuation of Study Treatment

If a subject must be permanently discontinued from study drug before the end of the double-blind treatment phase, this will not result in automatic withdrawal of the subject from the study, and the subject should continue to be followed for efficacy and safety outcomes (for details see Section 3.1).

A subject should be permanently discontinued from study drug if:

- The investigator believes that for safety reasons (ie, adverse event) it is in the best interest of the subject to stop study drug.
- The subject develops any condition which requires anticoagulation or thromboprophylaxis extending beyond the treatment phase of the study (eg, atrial fibrillation, VTE).
- The subject becomes pregnant.
- The subject has a fall in CrCl to below 20 mL/min or 2 consecutive measurements less than 30 mL/min at least 1 week apart (as calculated by Cockcroft-Gault formula, see Section 9.1.2) during the study.
- The subject requires hemofiltration or dialysis on a permanent basis
- The subject requests to discontinue study drug permanently
- The subject has a hemorrhagic stroke, or intracranial bleeding

If the subject permanently discontinues study drug before Day 45, he/she should be instructed to complete an unscheduled visit and the remaining scheduled visits, including the Day 7 and Day 21 visits (if not yet completed), and Day 45 (+4d) and Day 75 (\pm 5d) visits (Section 9.1.3). The Day 45 visit should be a clinic visit; the Day 75 visit may be a telephone visit.

The eCRF is to be completed to identify the reason for permanent discontinuation of study drug. The investigator will provide a narrative to describe any adverse events that occur up to the Day 75 (\pm 5d) visit. The appropriate adverse event or serious adverse event sections of the eCRF

are to be completed. If study drug is terminated for a serious adverse event, expedited reporting (within 24 hours) is also required as outlined in Section 12.3.2, Serious Adverse Events.

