4.4. Extent of Exposure

The number of subjects who take at least one dose of study drug will be provided for each treatment group.

Subject level duration of treatment exposure is defined as the duration between the first dose date and last dose date. Note that temporary study drug interruptions are included in this definition.

Duration of treatment exposure will be summarized by treatment.

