6.1. Bleeding Events

Unless otherwise stated, interim and final analyses of the principal safety outcome and non-major clinically relevant bleeding will be based on CEC adjudicated events.

The principal safety outcome is ISTH major bleeding. Treatments will be compared using the same Cox proportional hazards model as that for the primary efficacy outcome described earlier. The analysis will be based on the safety analysis set and on-treatment analysis phase. Treatments will also be compared using Anderson-Gill model for the time to multiple occurrences of the principal safety outcome. The analysis will be based on the safety analysis set and on-treatment analysis phase.

The homogeneity of treatment effects on the first occurrence of the principal safety outcome across subgroups defined in section 2.4 will be examined (at a 2-sided significance level of 0.05) via the test used for the primary efficacy outcome, based on the safety analysis set and on-treatment analysis phase.

Off-treatment major bleeding events, defined by the events from the 3 days after the last dose date, will be summarized by treatment groups.

Other safety outcomes are non-major clinically relevant bleeding and other bleeding.

Non-major clinically relevant bleeding will be analyzed based on time from randomization to the first occurrence. The same analysis as that for the principal safety outcome will be used.

All bleeding, other bleeding, bleeding by BARC classification as well as sub-categories of major bleeding, including critical sites, will be also summarized by treatment groups.

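### A major bleed more than 2 days after the last dose before an interruption enters the principal safety models only if study drug is later restarted

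*SAP*

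**What the plan says.** SAP 2.3 sets the window: "On-Treatment: This analysis phase includes all data from randomization to 2 days after the last dose of the study drug (inclusive". Subjects without an event in it "will be censored on the last dose + 2 or the last outcome-evaluation date whichever occurs first". Protocol 11.1.2 has the same definition.

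The last dose is one date per subject (SAP 2.1): "Last dose date: the date on which the last dose of study drug is taken by the subject". If that date has to be imputed, it is bounded below by, among others, "any complete temporary drug stop and re-start date", so a recorded restart carries the window forward. SAP 4.4 treats exposure the same way, as the span from first to last dose: "Note that temporary study drug interruptions are included in this definition".

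For ISTH major bleeding, SAP 6.1 says of both the Cox model for the first event and the Andersen-Gill model for repeated events: "The analysis will be based on the safety analysis set and on-treatment analysis phase". Later bleeds are handled descriptively: "Off-treatment major bleeding events, defined by the events from the 3 days after the last dose date, will be summarized by treatment groups".

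Protocol 10.2.1 provides for temporary interruption for procedures, for anticoagulation during re-hospitalization, for prohibited therapy, and after a major bleed that is not intracranial; after such a bleed, drug is to be resumed where possible. Protocol 10.2.3 lists among the reasons for permanent discontinuation: "The subject has a hemorrhagic stroke, or intracranial bleeding".

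**The concern.** Whether an event is on-treatment should be known when it happens. Here, for a bleed more than 2 days after the last pre-interruption dose, it is settled by a later fact: whether the subject takes study drug again. That fact is related to the bleed. A fatal bleed rules out a restart, and the protocol directs none after an intracranial bleed.

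The risk set has the matching problem. Interruption time beyond 2 days is counted only for subjects who restart, and a subject who restarts cannot have died during it. The model therefore includes person-time in which a fatal bleed could not be recorded.

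The same phase feeds several analyses: the principal safety outcome, non-major clinically relevant bleeding and the bleeding subgroup tests (SAP 6.1), sensitivity analysis (b) of the primary outcome (SAP 5.2.2), and the on-treatment bleeding rate in the third futility condition (SAP 3). The Andersen-Gill analysis is directly exposed: a first major bleed itself prompts interruption, so a re-bleed more than 2 days after the last dose counts only if drug is resumed. The trial was designed around the excess bleeding in earlier extended-prophylaxis studies (Protocol 1.1 and 1.1.5), so the safety hazard ratio should not turn on later restart.

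**Working it through.** The plan gives no figure on this point to reproduce. The check applies the rule to example records and then asks how many bleeds it could touch.

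**1. The rule on example records.** A bleed is on-treatment if bleed day ≤ last dose day + 2. The last dose before the interruption is Day 10 throughout.

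| Bleed | Restart | Last dose date | Window ends | In safety models | By Day 45 |
|---|---|---|---|---|---|
| Day 12, any severity | none | Day 10 | Day 12 | yes | yes |
| Day 14, non-fatal, not intracranial | Day 20, dosing to Day 45 | Day 45 | Day 47 | yes | yes |
| Day 14, non-fatal, not intracranial | none | Day 10 | Day 12 | no | yes |
| Day 14, fatal or intracranial | none | Day 10 | Day 12 | no | yes |

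The second and third rows are identical up to and including the bleed. Only the later restart separates them.

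**2. Time at risk.** An event-free subject with the same interruption who restarts on Day 20 contributes Days 13 to 19, which is 7 days more than 2 days after the last dose. A subject who never restarts is censored on Day 12 and contributes none of them.

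**3. Share of interruption bleeds counted.** Assume bleed onset is uniform over an interruption of L days, and that a fraction f of subjects bleeding after day 2 restart. Share counted = 2/L + (1 − 2/L) × f.

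| L (days) | f = 0 (fatal, or intracranial per protocol) | f = 0.8 | f = 1 |
|---|---|---|---|
| 5 | 40% | 88% | 100% |
| 7 | 29% | 86% | 100% |
| 10 | 20% | 84% | 100% |
| 14 | 14% | 83% | 100% |

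**4. Number of bleeds affected.** The only documentary inputs are about 12,000 subjects at 1:1 (6,000 per arm) and a window of 45 + 2 = 47 days. The rest is assumed: major bleeding 0.3% to 0.5%, 5% to 10% of subjects interrupted for 7 to 14 days, and a bleeding hazard during interruption of 1 to 5 times baseline.

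Bleeds per arm more than 2 days into an interruption = 6,000 × P(interrupt) × (length − 2) × (rate/47) × multiplier.

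- Low: 6,000 × 0.05 × 5 × (0.003/47) × 1 = 0.10.
- High: 6,000 × 0.10 × 12 × (0.005/47) × 5 = 3.83.

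As a share of all major bleeds:

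- Low: 0.10 out of 6,000 × 0.003 = 18, about 0.5%.
- High: the baseline 6,000 × 0.005 = 30 plus the excess from the multiplier, 3.83 × 4/5 = 3.06, gives 33.06; 3.83/33.06 = 11.6%.

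Off-drug share of time, if all restart: 0.05 × 5/47 = 0.53% to 0.10 × 12/47 = 2.55%.

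These are all the bleeds whose classification depends on restart, of any severity. If 10% to 30% of them were fatal or intracranial (an assumption; the documents give no figure), that subset would be about 0.01 to 1.1 per arm.

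**The case against.** A reader might infer that the principal safety analysis keeps the milder interruption bleeds and drops the fatal and intracranial ones. The documents do not support that. Any bleed up to 2 days after the last dose counts, fatal and intracranial ones included, as does the on-drug bleed that triggers an interruption. The split is by restart: a milder bleed without a restart is dropped too. What stands is narrower: beyond 2 days, a fatal bleed, or an intracranial one handled per protocol, has no route into the models.

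Nor are the excluded bleeds hidden. SAP 6.1 summarizes off-treatment major bleeds by arm. The primary benefit-risk analysis (SAP 7) uses the ITT set to Day 45 and covers major, critical-site and fatal bleeding with Kaplan-Meier rates. This stands, but the first is descriptive and the second is not intended for hypothesis testing. No Cox analysis of major bleeding over the Up-to-Day-45 phase is specified.

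The interim exposure is limited. The bleeding condition in SAP 3 is a judgment without a numerical cut-off, and the IDMC sees unblinded safety data and can ask for subject-level data (SAP 1.2).

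Sensitivity analysis (b) also uses the per-protocol set, which excludes subjects who took prohibited anticoagulants. That may remove many of the relevant interruptions.

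Finally, counting from first to last dose is a documented convention, applied identically in two blinded arms. That argues for keeping it as one analysis. It does not remove the dependence on a later restart.

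**Conclusion.** The point holds for bleeds more than 2 days after the last pre-interruption dose, and for the interruption time of subjects who restart. It follows from SAP 2.1, 2.3 and 6.1 without any assumption; the link to the type of bleed comes from Protocol 10.2.1 and 10.2.3.

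Its size rests wholly on assumed inputs: about 0.1 to 3.8 bleeds per arm, or 0.5% to 11.6% of major bleeds. The low end is trivial, and the high end needs every extreme input at once. A reader might go on to infer that the safety hazard ratio is biased in favour of rivaroxaban. The documents give no interruption frequency, length or restart rate by arm, so neither the size nor the direction of an effect can be derived. The change is still worth making: major bleeds are few, those affected can include the gravest, and the remedy is cheap.

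**What to change.** Keep the last dose + 2 days analysis and, in SAP 2.3 and 6.1, prespecify two analyses beside it.

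1. A Cox analysis of ISTH major bleeding in the safety set over the Up-to-Day-45 phase. It counts every Day 14 bleed in the table above, restarted or not.
2. An on-treatment Cox analysis that does not look ahead. An event is on-treatment if it occurs no later than 2 days after the latest preceding dose; (start, stop] risk intervals close 2 days after each temporary stop and reopen at restart. Apply it also to non-major clinically relevant bleeding and to sensitivity analysis (b), keeping the per-protocol set there.

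Both are needed. The second makes classification consistent but still leaves out the fatal or intracranial Day 14 bleed, and now leaves out the restarted one as well. Only the first brings these bleeds into a model.

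The cost is SAP wording and some programming. Interruptions are recorded on the eCRF (Protocol 6) and already enter the compliance formula (SAP 4.3). The second analysis has slightly fewer events and less time at risk. The first includes off-drug bleeds and, for a subject dosed to Day 45, stops 2 days short of the on-treatment window. No clinical rule changes.
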